  - c. Metformin 1700-2550 mg + glibenclamide 5 mg  $\rightarrow$  metformin 1700 mg + glibenclamide 2.5 mg
  - d. Metformin 1700-2550 mg + glibenclamide 10 mg  $\rightarrow$  metformin 1700 mg + glibenclamide 5 mg
- 14. Metformin and glibenclamide without problems, nonadherent, took glibenclamide yesterday  $\rightarrow$  same as #13
- 15. Metformin and glibenclamide without problems, adherent, did not take glibenclamide yesterday  $\rightarrow$  metformin 1700 mg

<sup>18 Numbers in parentheses refer to the relevant measurements for patients who have relaxed glycemic goals (A1c ≤8, FBG 90-150, PPBG <200)

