#### [name]

- 16. Metformin and glibenclamide without problems, nonadherent, did not take glibenclamide yesterday  $\rightarrow$ metformin 1700 ma
- 17. Metformin and glibenclamide, problems with metformin, adherent, took glibenclamide yesterday a. Agrees to take metformin
  - - Metformin 850 mg + glibenclamide 2.5mg → metformin 850 mg
    - Metformin 850 mg + glibenclamide 5 mg  $\rightarrow$  metformin 850 mg + glibenclamide 2.5 mg ii. Metformin 850 mg + glibenclamide 10 mg  $\rightarrow$  metformin 850 mg + glibenclamide 5 mg iii.
  - b Refuses to take metformin
    - Metformin 850 mg + glibenclamide 2.5 mg → stop medications, recheck A1c in 3 months i.
    - Metformin 850 mg + glibenclamide 5 mg  $\rightarrow$  glibenclamide 2.5 mg ii.
    - iii. Metformin 850 mg + glibenclamide 10 mg  $\rightarrow$  glibenclamide 5 mg
  - c. Metformin 1700 mg + glibenclamide 2.5 mg  $\rightarrow$  metformin 850 mg
  - d. Metformin 1700 mg + glibenclamide 5 mg  $\rightarrow$  metformin 850 mg + glibenclamide 2.5
  - e. Metformin 1700 mg + glibenclamide 10 mg  $\rightarrow$  metformin 850 mg + glibenclamide 5 mg
  - f. Metformin 2550 mg + glibenclamide 2.5 mg  $\rightarrow$  metformin 1700 mg
  - g. Metformin 2550 mg + glibenclamide 5 mg  $\rightarrow$  metformin 1700 mg + glibenclamide 2.5 mg
  - h. Metformin 2550 mg + glibenclamide 10 mg  $\rightarrow$  metformin 1700 mg + glibenclamide 5 mg
- 18. Metformin and glibenclamide, problems with metformin, nonadherent, took glibenclamide yesterday  $\rightarrow$ same as #17
- 19. Metformin and glibenclamide, problems with metformin, adherent, did not take glibenclamide yesterday
  - a. Metformin 850 mg + glibenclamide any dose, agrees to take metformin  $\rightarrow$  metformin 850 mg b. Metformin 850 mg + glibenclamide any dose, refuses to take metformin → stop medications,
  - recheck A1c in 3 months
  - c. Metformin 1700 mg + glibenclamide any dose  $\rightarrow$  metformin 850 mg
  - d. Metformin 2550 mg + glibenclamide any dose  $\rightarrow$  metformin 1700 mg
- 20. Metformin and glibenclamide, problems with metformin, nonadherent, did not take glibenclamide vesterdav  $\rightarrow$  same as #19
- 21. Metformin and glibenclamide, hypoglycemia or hypoglycemia symptoms, adherent, took glibenclamide yesterday
  - a. Metformin 850 mg + glibenclamide any dose  $\rightarrow$  metformin 1700 mg
  - b. Metformin 1700 mg + glibenclamide 2.5-5 mg → metformin 1700 mg

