  - c. Metformin 1700 mg + glibenclamide 10 mg → metformin 1700 mg + glibenclamide 2.5 mg
  - d. Metformin 2550 mg + glibenclamide 2.5-5 mg  $\rightarrow$  metformin 2550 mg
  - e. Metformin 2550 mg + glibenclamide 10 mg  $\rightarrow$  metformin 2550 mg + glibenclamide 5 mg
- 22. Metformin and glibenclamide, hypoglycemia or hypoglycemia symptoms, nonadherent, took glibenclamide vesterday
  - a. Metformin 850 mg + glibenclamide any dose → metformin 1700 mg
  - b. Metformin 1700-2500 mg + glibenclamide 2.5-5 mg → metformin 1700 mg
  - c. Metformin 1700-2550 mg + glibenclamide 10 mg  $\rightarrow$  metformin 1700 mg + glibenclamide 2.5 mg
- 23. Metformin and glibenclamide, hypoglycemia or hypoglycemia symptoms, adherent, did not take glibenclamide yesterday
  - a. Metformin 850-1700 mg + glibenclamide any dose  $\rightarrow$  metformin 1700 mg
  - b. Metformin 2550 mg + glibenclamide any dose  $\rightarrow$  metformin 2550 mg
- 24. Metformin and glibenclamide, hypoglycemia or hypoglycemia symptoms, nonadherent, did not take glibenclamide yesterday  $\rightarrow$  metformin 1700 mg
- 25. Metformin and glibenclamide, problems with metformin, hypoglycemia or hypoglycemia symptoms, adherent, took glibenclamide yesterday

[name]

- a. Agrees to take metformin
  - i. Metformin 850 mg + glibenclamide 2.5-5 mg → metformin 850 mg
- ii. Metformin 850 mg + glibenclamide 10 mg  $\rightarrow$  metformin 850 mg + glibenclamide 2.5 mg b. Refuses to take metformin
  - i. Metformin 850 mg + glibenclamide 2.5-5 mg  $\rightarrow$  stop medications, recheck A1c in 3 months
  - ii. Metformin 850 mg + glibenclamide 10 mg  $\rightarrow$  glibenclamide 2.5 mg
- c. Metformin 1700 mg + glibenclamide 2.5-5 mg → metformin 850 mg
- d. Metformin 1700 mg + glibenclamide 10 mg  $\rightarrow$  metformin 850 mg + glibenclamide 2.5 mg
- e. Metformin 2550 mg + glibenclamide 2.5-5 mg  $\rightarrow$  metformin 1700 mg
- f. Metformin 2550 mg + glibenclamide 10 mg → metformin 1700 mg + glibenclamide 2.5 mg
- 26. Metformin and glibenclamide, problems with metformin, hypoglycemia or hypoglycemia symptoms, nonadherent, took glibenclamide yesterday → same as #25
- 27. Metformin and glibenclamide, problems with metformin, hypoglycemia or hypoglycemia symptoms, adherent, did not take glibenclamide yesterday
  - a. Metformin 850 mg + glibenclamide any dose, agrees to take metformin  $\rightarrow$  metformin 850 mg

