- 12. Glibenclamide with hypoglycemia symptoms, previous problems with metformin did not take yesterday
  - a. Agrees to take metformin  $\rightarrow$  metformin 850 mg
  - b. Refuses to take metformin
    - i. Glibenclamide 2.5-5 mg  $\rightarrow$  stop medications, check A1c when next indicated
    - ii. Glibenclamide 10 mg  $\rightarrow$  glibenclamide 2.5 mg
- 13. Metformin and glibenclamide without problems, adherent, took glibenclamide yesterday  $\rightarrow$  continue current doses
- 14. Metformin and glibenclamide without problems, nonadherent, took glibenclamide yesterday
  - a. Metformin any dose + glibenclamide 2.5 mg  $\rightarrow$  metformin 1700 mg
  - b. Metformin any dose + glibenclamide 5 mg  $\rightarrow$  metformin 1700 mg + glibenclamide 2.5 mg
  - c. Metformin any dose + glibenclamide 10 mg  $\rightarrow$  metformin 1700 mg + glibenclamide 5 mg
- 15. Metformin and glibenclamide without problems, adherent, did not take glibenclamide yesterday
  - a. Metformin any dose + glibenclamide 2.5mg  $\rightarrow$  metformin current dose
  - b. Metformin any dose + glibenclamide 5 mg  $\rightarrow$  metformin current dose + glibenclamide 2.5 mg
  - c. Metformin any dose + glibenclamide 10 mg  $\rightarrow$  metformin current dose + glibenclamide 5 mg
- 16. Metformin and glibenclamide without problems, nonadherent, did not take glibenclamide yesterday
  - a. Metformin all doses + glibenclamide 2.5-5 mg  $\rightarrow$  metformin 1700 mg
  - b. Metformin all doses + glibenclamide 10 mg  $\rightarrow$  metformin 1700 mg + glibenclamide 2.5 mg
- 17. Metformin and glibenclamide, problems with metformin, adherent, took glibenclamide yesterday
  - a. Metformin 850 mg + any dose of glibenclamide, agrees to take metformin → continue current doses
  - b. Metformin 850 mg + any dose of glibenclamide, refuses to take metformin  $\rightarrow$  continue current dose of glibenclamide
  - c. Metformin 1700 mg + glibenclamide any dose  $\rightarrow$  metformin 850 mg + glibenclamide current dose
  - d. Metformin 2550 mg + glibenclamide any dose → metformin 1700 mg + glibenclamide current dose
- 18. Metformin and glibenclamide, problems with metformin, nonadherent, took glibenclamide yesterday → same as #17
- Metformin and glibenclamide, problems with metformin, adherent, did not take glibenclamide yesterday

   Agrees to take metformin
  - i. Metformin 850 mg + glibenclamide 2.5 mg  $\rightarrow$  metformin 850 mg

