22. Metformin and glibenclamide, hypoglycemia symptoms, nonadherent, took glibenclamide yesterday a. Metformin 850 mg + glibenclamide 2.5 mg  $\rightarrow$  metformin 1700 mg

- b. Metformin 850 mg + glibenclamide 5 mg → metformin 1700 mg + glibenclamide 2.5 mg
- c. Metformin 850 mg + glibenclamide 10 mg  $\rightarrow$  metformin 1700 mg + glibenclamide 5 mg
- d. Metformin 1700-2550 mg + glibenclamide 2.5 mg  $\rightarrow$  metformin 1700 mg
- e. Metformin 1700-2550 mg + glibenclamide 5 mg → metformin 1700 mg + glibenclamide 2.5 mg
- f. Metformin 1700-2550 mg + glibenclamide 10 mg  $\rightarrow$  metformin 1700 mg + glibenclamide 5 mg
- 23. Metformin and glibenclamide, hypoglycemia symptoms, adherent, did not take glibenclamide yesterday a. Metformin 850-1700 mg + glibenclamide any dose  $\rightarrow$  metformin 1700 mg
  - b. Metformin 2550 mg + glibenclamide any dose  $\rightarrow$  metformin 2550 mg

24. Metformin and glibenclamide, hypoglycemia symptoms, nonadherent, did not take glibenclamide yesterday → metformin 1700 mg

25. Metformin and glibenclamide, problems with metformin, hypoglycemia symptoms, adherent, took glibenclamide yesterday

a. Agrees to take metformin

i. Metformin 850 mg + glibenclamide 2.5 mg → metformin 850 mg

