  - g. Metformin 2550 mg + glibenclamide 2.5 mg  $\rightarrow$  metformin 2550 mg
  - h. Metformin 2550 mg + glibenclamide 5 mg  $\rightarrow$  metformin 2550 mg + glibenclamide 2.5 mg
  - i. Metformin 2550 mg + glibenclamide 10 mg  $\rightarrow$  metformin 2550 mg + glibenclamide 5 mg
- 22. Metformin and glibenclamide, hypoglycemia symptoms, nonadherent, took glibenclamide yesterday  $\rightarrow$  same as #16
- 23. Metformin and glibenclamide, hypoglycemia symptoms, adherent, did not take glibenclamide yesterday → same as #16
- 24. Metformin and glibenclamide, hypoglycemia symptoms, nonadherent, did not take glibenclamide yesterday
  - a. Metformin all doses + glibenclamide 2.5-5 mg  $\rightarrow$  metformin current dose
- b. Metformin all doses + glibenclamide 10 mg → metformin current dose + glibenclamide 2.5 mg
   25. Metformin and glibenclamide, problems with metformin, hypoglycemia symptoms, adherent, took glibenclamide yesterday
  - a. Agrees to take metformin
    - i. Metformin 850 mg + glibenclamide 2.5 mg  $\rightarrow$  metformin 850 mg
    - ii. Metformin 850 mg + glibenclamide 5 mg  $\rightarrow$  metformin 850 mg + glibenclamide 2.5 mg
    - iii. Metformin 850 mg + glibenclamide 10 mg  $\rightarrow$  metformin 850 mg + glibenclamide 5 mg

[name]

- b. Refuses to take metformin
  - i. Metformin 850 mg + glibenclamide 2.5 mg  $\rightarrow$  MD consult
  - ii. Metformin 850 mg + glibenclamide 5 mg  $\rightarrow$  glibenclamide 2.5 mg
  - iii. Metformin 850 mg + glibenclamide 10 mg  $\rightarrow$  glibenclamide 5 mg
- c. Metformin 1700 mg + glibenclamide 2.5 mg  $\rightarrow$  metformin 850 mg
- d. Metformin 1700 mg + glibenclamide 5 mg  $\rightarrow$  metformin 850 mg + glibenclamide 2.5 mg
- e. Metformin 1700 mg + glibenclamide 10 mg  $\rightarrow$  metformin 850 mg + glibenclamide 5 mg
- f. Metformin 2550 mg + glibenclamide 2.5 mg  $\rightarrow$  metformin 1700 mg
- g. Metformin 2550 mg + glibenclamide 5 mg → metformin 1700 mg + glibenclamide 2.5 mg
- h. Metformin 2550 mg + glibenclamide 10 mg  $\rightarrow$  metformin 1700 mg + glibenclamide 5 mg
- 26. Metformin and glibenclamide, problems with metformin, hypoglycemia symptoms, nonadherent, took glibenclamide yesterday  $\rightarrow$  same as #25
- 27. Metformin and glibenclamide, problems with metformin, hypoglycemia symptoms, adherent, did not take glibenclamide yesterday
  - a. Agrees to take metformin
    - i. Metformin 850 mg + glibenclamide 2.5-5 mg → metformin 850 mg

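### Appendix 10: in 8 of 24 states at metformin 850 mg plus glibenclamide, a higher glucose band gives less metformin with the same glibenclamide

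*Combined protocol and SAP*

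**What the plan says.** Appendix 10 is the rule that the application follows at monthly visits when A1c is not measured. It has four titration bands, named here by their fasting limits: below 80, 80-130, 130-180 and 180-400 mg/dL. Patients with relaxed goals have limits of 90, 150 and 200 in place of 80, 130 and 180, and each band has a postprandial equivalent. For patients on both drugs without metformin problems, rows 13-16 (no hypoglycemia symptoms) and 21-24 (symptoms) split by adherence and by whether glibenclamide was taken the day before.

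The rows at issue, for a patient on metformin 850 mg:

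- Row 15, "Metformin and glibenclamide without problems, adherent, did not take glibenclamide yesterday": below 80, metformin 1700 mg alone. At 80-130, row 15a (glibenclamide 2.5 mg) leaves metformin as it is and stops glibenclamide.
- Row 16, "Metformin and glibenclamide without problems, nonadherent, did not take glibenclamide yesterday": below 80, 1700 mg alone. At 80-130, row 16a, "Metformin all doses + glibenclamide 2.5-5 mg", again gives 1700 mg alone. At 130-180, metformin stays as it is and glibenclamide drops one step.
- Row 22, "Metformin and glibenclamide, hypoglycemia symptoms, nonadherent, took glibenclamide yesterday": at 80-130, 1700 mg with glibenclamide down one step. At 130-180, the row refers back to row 16, so metformin stays at 850 mg. At 180-400, 1700 mg again.
- Row 23, "Metformin and glibenclamide, hypoglycemia symptoms, adherent, did not take glibenclamide yesterday": in the two lowest bands row 23a, "Metformin 850-1700 mg + glibenclamide any dose", gives 1700 mg alone. At 130-180 it refers back to row 16.
- Row 24, "Metformin and glibenclamide, hypoglycemia symptoms, nonadherent, did not take glibenclamide yesterday": 1700 mg alone in the two lowest bands. At 130-180, metformin stays at 850 mg.

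Section 6.5 makes 1700 mg the target dose and assigns 850 mg to patients who cannot tolerate it.

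**The concern.** In a titration table, a higher glucose should not bring less of one drug while the other is unchanged. Here it does, for patients who report no trouble with the drug being held down. Community health workers act on these outputs as standing orders, and the physician reviews them afterwards (Sections 2.1 and 7.4.1).

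Section 2.7.2 relies on testing every scenario before use, and Section 4.1.3 counts incorrect application recommendations as a primary safety endpoint. The documents do not say what the reference for correctness is. If it is this table, the affected states will pass testing and will not be counted as incorrect.

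The states can be reached. Enrollment row 10a, for A1c from 6.5 to goal, puts patients without problems on metformin 850 mg plus their current glibenclamide (Appendix 8). Row 3c of the monthly 130-180 band creates 850 mg plus 2.5 mg.

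**Working it through.** **Inputs.** Rows 13-16 and 21-24 of the four Appendix 10 bands, with current metformin 850 mg and current glibenclamide 2.5, 5 or 10 mg.

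**States.** 2 (adherent or not) × 2 (took glibenclamide yesterday or not) × 2 (hypoglycemia symptoms or not) = 8 rows; 8 × 3 glibenclamide doses = 24 states.

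**Test.** A state is inverted if a lower band gives metformin 1700 mg, a higher band gives 850 mg, and the glibenclamide output is the same in both.

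**Result.** The inverted states, with outputs as metformin + glibenclamide in mg/day:

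| Row | Current glibenclamide | <80 | 80-130 | 130-180 | 180-400 |
|---|---|---|---|---|---|
| 15 | 2.5 | 1700 + 0 | 850 + 0 | 850 + 2.5 | 850 + 2.5 |
| 16 | 2.5 | 1700 + 0 | 1700 + 0 | 850 + 0 | 850 + 2.5 |
| 22 | 2.5 | 1700 + 0 | 1700 + 0 | 850 + 0 | 1700 + 0 |
| 22 | 5 | 1700 + 0 | 1700 + 2.5 | 850 + 2.5 | 1700 + 2.5 |
| 22 | 10 | 1700 + 0 | 1700 + 5 | 850 + 5 | 1700 + 5 |
| 23 | 2.5 | 1700 + 0 | 1700 + 0 | 850 + 0 | 1700 + 0 |
| 24 | 2.5 | 1700 + 0 | 1700 + 0 | 850 + 0 | 1700 + 0 |
| 24 | 5 | 1700 + 0 | 1700 + 0 | 850 + 0 | 1700 + 2.5 |

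By row: 1 + 1 + 3 + 1 + 2 = 8 of 24. Rows 13, 14 and 21 contribute none.

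By band pair (a state can count in more than one): <80 against 80-130, 1 state; <80 against 130-180, 5; 80-130 against 130-180, 7; any band against 180-400, 0. The difference is always 1700 − 850 = 850 mg/day.

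**Elsewhere.** The 24 states at metformin 850 mg with metformin problems (rows 17-20 and 25-28) contain no inversion, so the count over all combination rows at 850 mg is 8 of 48. At metformin 1700 or 2550 mg there is none.

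**Which band is out of line.** Row 21, the adherent patient with symptoms who took glibenclamide, gives 1700 mg in all four bands. Rows 22-24 give 1700 mg in three bands and 850 mg only at 130-180. Row 22 metformin therefore runs 1700, 1700, 850, 1700 mg.

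**After the fix.** Rows 16, 22, 23 and 24 at 130-180 are 4 × 3 = 12 outputs, and row 15a at 80-130 is 1 more: 13 changed outputs. Rows 22-24 then give 1700 mg in every band. Row 15 with glibenclamide 2.5 mg becomes 1700 + 0, 1700 + 0, 850 + 2.5, 850 + 2.5. Row 16 with 2.5 mg becomes 1700 + 0 in three bands, then 850 + 2.5. No pair with equal glibenclamide is inverted.

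**The case against.** The 1700 mg outputs have a natural explanation. It is the target dose, and metformin can replace glibenclamide that is being stopped. That accounts for the lower bands. It does not account for leaving the same patient at 850 mg at a higher glucose when glibenclamide changes by the same amount.

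Nonadherence does not explain the order either. Rows 15 and 23 are adherent patients, and nonadherent rows 22 and 24 are raised to 1700 mg in every band except 130-180.

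Some patients may be on 850 mg because they did not tolerate more, and holding that dose could be deliberate. But these rows are for patients without metformin problems, and the table raises the same patients to 1700 mg in other bands. This remains a reason for clinical confirmation of the fix.

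Three stronger readings are tempting and are not supported:

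- **21 of 24.** Without the equal-glibenclamide condition, 21 of 24 states show 1700 mg below 850 mg. Many of those are partly explained by glibenclamide being stopped or lowered more in the lower band. Eight is the defensible count.
- **Hypoglycemia.** A reader might infer a safety hazard from 1700 mg at a glucose below 80. Section 2.7.1 ties hypoglycemia to glibenclamide, which is equal in every compared pair.
- **Breach of Section 2.7.2.** A reader might say that raising metformin at low glucose breaks the rule limiting monthly up-titration to glucose well above goal. In the inverted states glibenclamide is lowered or stopped at the same visit, so an overall up-titration is not shown. Nor would that rule explain 1700 mg below 850 mg.

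**Conclusion.** The table is wrong as written in 8 of 24 states, and the error is minor. The count rests on reading Appendix 10 literally, including the 130-180 cross-references from rows 22 and 23 to row 16. The documents do not show whether those references are a drafting slip.

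No effect on A1c, on the primary analyses or on hypoglycemia is shown. The documents do not say how many patients take metformin 850 mg plus glibenclamide, so the number of affected visits is unknown. Physician review within one week of each visit limits harm.

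**What to change.** For patients on metformin 850 mg:

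- in the 130(150)-180(200) band, set metformin to 1700 mg in rows 22, 23 and 24, matching row 21 of that band and rows 22-24 of the other three, and in row 16;
- in the 80(90)-130(150) band, set row 15a to metformin 1700 mg.

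Leave every glibenclamide output, and every output at metformin 1700 or 2550 mg, unchanged. Re-test these branches in the application.

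Cost: five table rows and their re-testing. All 13 changed outputs add 850 mg/day of metformin at a visit where glibenclamide is lowered or stopped, as row 21 already does. The medical director should confirm this direction, especially for rows 15a and 16, which have less support from neighbouring rows. In row 16, metformin still falls from 1700 to 850 mg at 180-400, but there with more glibenclamide.

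The alternative, holding 850 mg in the lower bands of rows 15, 16 and 22-24, also removes the inversions. It changes 27 outputs, moves away from the target dose, and breaks the present uniform rule below 80, where all eight rows give 1700 mg alone. It also leaves patients who stay nonadherent on 850 mg alone even at 180-400, because row 2 of that band makes no change.

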#### [name]

- 16. Metformin and glibenclamide without problems, nonadherent, did not take glibenclamide yesterday  $\rightarrow$ metformin 1700 ma
- 17. Metformin and glibenclamide, problems with metformin, adherent, took glibenclamide yesterday a. Agrees to take metformin
  - - Metformin 850 mg + glibenclamide 2.5mg → metformin 850 mg
    - Metformin 850 mg + glibenclamide 5 mg  $\rightarrow$  metformin 850 mg + glibenclamide 2.5 mg ii. Metformin 850 mg + glibenclamide 10 mg  $\rightarrow$  metformin 850 mg + glibenclamide 5 mg iii.
  - b Refuses to take metformin
    - Metformin 850 mg + glibenclamide 2.5 mg → stop medications, recheck A1c in 3 months i.
    - Metformin 850 mg + glibenclamide 5 mg  $\rightarrow$  glibenclamide 2.5 mg ii.
    - iii. Metformin 850 mg + glibenclamide 10 mg  $\rightarrow$  glibenclamide 5 mg
  - c. Metformin 1700 mg + glibenclamide 2.5 mg  $\rightarrow$  metformin 850 mg
  - d. Metformin 1700 mg + glibenclamide 5 mg  $\rightarrow$  metformin 850 mg + glibenclamide 2.5
  - e. Metformin 1700 mg + glibenclamide 10 mg  $\rightarrow$  metformin 850 mg + glibenclamide 5 mg
  - f. Metformin 2550 mg + glibenclamide 2.5 mg  $\rightarrow$  metformin 1700 mg
  - g. Metformin 2550 mg + glibenclamide 5 mg  $\rightarrow$  metformin 1700 mg + glibenclamide 2.5 mg
  - h. Metformin 2550 mg + glibenclamide 10 mg  $\rightarrow$  metformin 1700 mg + glibenclamide 5 mg
- 18. Metformin and glibenclamide, problems with metformin, nonadherent, took glibenclamide yesterday  $\rightarrow$ same as #17
- 19. Metformin and glibenclamide, problems with metformin, adherent, did not take glibenclamide yesterday
  - a. Metformin 850 mg + glibenclamide any dose, agrees to take metformin  $\rightarrow$  metformin 850 mg b. Metformin 850 mg + glibenclamide any dose, refuses to take metformin → stop medications,
  - recheck A1c in 3 months
  - c. Metformin 1700 mg + glibenclamide any dose  $\rightarrow$  metformin 850 mg
  - d. Metformin 2550 mg + glibenclamide any dose  $\rightarrow$  metformin 1700 mg
- 20. Metformin and glibenclamide, problems with metformin, nonadherent, did not take glibenclamide vesterdav  $\rightarrow$  same as #19
- 21. Metformin and glibenclamide, hypoglycemia or hypoglycemia symptoms, adherent, took glibenclamide yesterday
  - a. Metformin 850 mg + glibenclamide any dose  $\rightarrow$  metformin 1700 mg
  - b. Metformin 1700 mg + glibenclamide 2.5-5 mg → metformin 1700 mg
  - c. Metformin 1700 mg + glibenclamide 10 mg → metformin 1700 mg + glibenclamide 2.5 mg
  - d. Metformin 2550 mg + glibenclamide 2.5-5 mg  $\rightarrow$  metformin 2550 mg
  - e. Metformin 2550 mg + glibenclamide 10 mg  $\rightarrow$  metformin 2550 mg + glibenclamide 5 mg
- 22. Metformin and glibenclamide, hypoglycemia or hypoglycemia symptoms, nonadherent, took glibenclamide vesterday
  - a. Metformin 850 mg + glibenclamide any dose → metformin 1700 mg
  - b. Metformin 1700-2500 mg + glibenclamide 2.5-5 mg → metformin 1700 mg
  - c. Metformin 1700-2550 mg + glibenclamide 10 mg  $\rightarrow$  metformin 1700 mg + glibenclamide 2.5 mg
- 23. Metformin and glibenclamide, hypoglycemia or hypoglycemia symptoms, adherent, did not take glibenclamide yesterday
  - a. Metformin 850-1700 mg + glibenclamide any dose  $\rightarrow$  metformin 1700 mg
  - b. Metformin 2550 mg + glibenclamide any dose  $\rightarrow$  metformin 2550 mg
- 24. Metformin and glibenclamide, hypoglycemia or hypoglycemia symptoms, nonadherent, did not take glibenclamide yesterday  $\rightarrow$  metformin 1700 mg
- 25. Metformin and glibenclamide, problems with metformin, hypoglycemia or hypoglycemia symptoms, adherent, took glibenclamide yesterday

[name]

- a. Agrees to take metformin
  - i. Metformin 850 mg + glibenclamide 2.5-5 mg → metformin 850 mg
- ii. Metformin 850 mg + glibenclamide 10 mg  $\rightarrow$  metformin 850 mg + glibenclamide 2.5 mg b. Refuses to take metformin
  - i. Metformin 850 mg + glibenclamide 2.5-5 mg  $\rightarrow$  stop medications, recheck A1c in 3 months
  - ii. Metformin 850 mg + glibenclamide 10 mg  $\rightarrow$  glibenclamide 2.5 mg
- c. Metformin 1700 mg + glibenclamide 2.5-5 mg → metformin 850 mg
- d. Metformin 1700 mg + glibenclamide 10 mg  $\rightarrow$  metformin 850 mg + glibenclamide 2.5 mg
- e. Metformin 2550 mg + glibenclamide 2.5-5 mg  $\rightarrow$  metformin 1700 mg
- f. Metformin 2550 mg + glibenclamide 10 mg → metformin 1700 mg + glibenclamide 2.5 mg
- 26. Metformin and glibenclamide, problems with metformin, hypoglycemia or hypoglycemia symptoms, nonadherent, took glibenclamide yesterday → same as #25
- 27. Metformin and glibenclamide, problems with metformin, hypoglycemia or hypoglycemia symptoms, adherent, did not take glibenclamide yesterday
  - a. Metformin 850 mg + glibenclamide any dose, agrees to take metformin  $\rightarrow$  metformin 850 mg
  - b. Metformin 850 mg + glibenclamide any dose, refuses to take metformin → stop medications, recheck A1c in 3 months
  - c. Metformin 1700 mg + glibenclamide any dose  $\rightarrow$  metformin 850 mg
  - d. Metformin 2550 mg + glibenclamide any dose  $\rightarrow$  metformin 1700 mg
- 28. Metformin and glibenclamide, problems with metformin, hypoglycemia or hypoglycemia symptoms, nonadherent, did not take glibenclamide yesterday → same as #27

